## **Missing Date Information for Adverse Events and Concomitant Medications**

The following conventions will be used to impute missing portions of dates for adverse events and concomitant medications. Note that the imputed values outlined here may not always provide the most conservative date.

### **Missing Start Dates**

- If the day is unknown, then:
  - If the month and year match the first dose of investigational product start date month and year in this study, then impute the day of the first dose date.
  - Otherwise, assign the first day of the month.
- If the month is unknown, then:
  - If the year matches the year of the first dose of investigational product date in this study, then impute the month and day of the first dose date in this study.
  - Otherwise, assign ‘January’
- If the year is unknown, then the date will not be imputed and will be assigned a missing value.

If the imputed start date is earlier than birth date, then birth date will be used.

### **Missing Stop Dates**

- If the day is unknown, then assign the last day of the month.
- If the month is unknown, then assign ‘December.’
- If the year is unknown, then the date will not be imputed and will be assigned a missing value.
- If the resulting end date is after the date of study completion / discontinuation, set the imputed end date as the date of study completion / discontinuation.

## **Missing Causal Relationship to Investigational Product for Adverse Events**

If the causal relationship to the investigational product is missing for an AE that started on or after the date of the first dose of double-blind investigational product, a causality of yes will

be assigned. The imputed values for causal relationship to investigational product will be used for the incidence summary; the values will be shown as missing in the data listings.

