### **7.4.6 Blinding**

The study drug will be administered open-label; no study participants will be blinded to study treatment.

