#### **7.5.4.9 Adverse Events**

All AEs will be recorded from the time the subject signs the informed consent until 30 days after the last dose of study drug. The determination, evaluation, reporting, and follow-up of AEs will be performed as outlined in Section 8.5. At each visit subjects will be asked about any new or ongoing AEs since the previous visit. Assessments of AEs will occur at each study visit.

Clinically significant changes from study baseline in physical examination findings, weight, vital signs, and clinical laboratory parameters, will be recorded as AEs or SAEs, if appropriate.

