### 3.5 Randomization and Blinding Method of Assigning Subjects to Treatment Groups

Not applicable. This is an open label study without randomization of treatment assignment.

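### Two adverse-event imputation rules in SAP 7.2 are wrong as written: missing causality hangs on a double-blind first dose this trial does not have, and a partial start date can be imputed later than the event's known stop date

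*SAP*

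**What the plan says.** **Missing causality.** SAP 7.2 (Missing Causal Relationship to Investigational Product for Adverse Events) imputes a positive relationship for an event that "started on or after the date of the first dose of double-blind investigational product, a causality of yes will" be assigned. On where the result goes, it says: "The imputed values for causal relationship to investigational product will be used for the incidence summary".

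**Blinding.** SAP 3.5 states: "This is an open label study without randomization of treatment assignment". Protocol 7.4.6 states: "The study drug will be administered open-label; no study participants will be blinded to study treatment". Protocol 7.4.5 confirms a single treatment group.

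**Partial start dates.** In SAP 7.2 (Missing Start Dates), if only the day is unknown and the month and year are those of the first dose, "then impute the day of the first dose date". If the month is unknown and the year is that of the first dose, "then impute the month and day of the first dose date in this study". Otherwise the first of the month, or January, is used. The one limit on the result is that it may not precede birth. The companion rule for stop dates limits an imputed stop only by study completion or discontinuation. Neither rule compares start with stop.

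**Use of these values.** SAP 8.8.1 tabulates subject incidence of TEAEs and also summarises SAEs, treatment-related TEAEs and treatment-related SAEs.

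**The concern.** Safety and tolerability form part of the primary objective, and Protocol 7.6 leaves the handling of missing data to the SAP. Each of these rules, followed to the letter, gives a result that its author cannot have wanted.

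The causality rule is meant to be conservative: when the investigator's assessment is missing, count the event as related. Tied to a dose that no child receives, it does the reverse. SAP 7.1 treats missing data as missing unless stated otherwise, so the causality stays blank and the event is absent from the treatment-related counts.

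The start-date rule is also meant to be conservative, and it usually is. It fails where the record already shows that the event was over before dosing. Such events can occur, because Protocol 7.5.4.9 collects adverse events from consent and screening may begin up to 30 days before Baseline. The rule then creates an interval that ends before it begins and places the start on the first infusion day.

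The first error lowers the count of related events; the second raises the count of treatment-emergent events.

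**Working it through.** The documents give no figure on this point to reproduce. The check is to apply the rules literally to dates. The dates below are assumed for illustration: first dose 20 June 2015.

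**Start-date rule**

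| Recorded start | Known stop | Start as written | Start with a stop-date check |
|---|---|---|---|
| day unknown, June 2015 | 10 June | 20 June, 10 days after the stop; dated as a TEAE | 1 June; not a TEAE |
| day and month unknown, 2015 | 10 June | 20 June, 10 days after the stop; dated as a TEAE | 1 January; not a TEAE |
| day unknown, June 2015 | 25 June | 20 June; TEAE | 20 June; TEAE (unchanged) |
| day unknown, May 2015 | 10 June | 1 May; not a TEAE | 1 May; not a TEAE (unchanged) |

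The first two rows are not special cases. Whenever the first-dose branch is used, the imputed start equals the first-dose date, so any known stop before that date must precede the imputed start. An enumeration for 2015 took every first-dose day, every pre-dose onset in the same month within 30 days, and every stop from onset to the day before dosing. A month of n days contributes (n − 1)n(n + 1)/6 combinations:

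- 31 days: 30 × 31 × 32 / 6 = 4,960, for 7 months = 34,720
- 30 days: 29 × 30 × 31 / 6 = 4,495, for 4 months = 17,980
- 28 days: 27 × 28 × 29 / 6 = 3,654, for 1 month
- Total: 34,720 + 17,980 + 3,654 = 56,354

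All 56,354 gave a start after the stop.

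**Reach.** Assume that first-dose days are spread evenly over the calendar (2015 and 2016 used). About 49% of the 30 pre-dose days then fall in the first-dose month: 0 of 30 if dosing starts on the 1st, 14 on the 15th, 29 on the 30th. About 96% fall in the first-dose year. These are shares of days on which the rule could apply, not shares of events.

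**Causality rule.** Take two events with missing causality, with onset on 20 June and 1 August 2015. As written, neither is imputed, because there is no double-blind dose date to compare with. With the first dose of UX003 in this study as the reference, both become related.

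**The two rules together.** Take the first row of the table, with causality also missing:

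- As written: dated as a TEAE, not counted as related.
- Causality trigger corrected only: the imputed start of 20 June meets the trigger, so the event counts as a treatment-related TEAE although it ended before any dose in this study.
- Both corrected: start 1 June, not a TEAE, causality not imputed.

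**The case against.** **The word double-blind is template carry-over.** There is one product and one arm, and the date and TEAE rules refer to the first dose in this study. A programmer would probably read the trigger that way. This is likely, and it makes the practical risk small, but it does not make the text usable as written. Deleting the adjective alone would still leave out the qualifier in this study, which matters for children already treated under an emergency IND. That ambiguity is narrow: it touches only events between consent and the first in-study dose.

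**The TEAE definition already protects against the date error.** SAP 8.8.1 excludes an event that was present before the first dose unless it worsened, so an event with a recorded pre-dose stop fails the definition on review. This stands as far as it goes. It does not help if the flag is derived from the imputed start, and no rule prevents that. The SAP's caveat that imputed dates may not be the most conservative does not resolve a start later than its stop.

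**Such records should be rare.** The protocol says: "At each visit subjects will be asked about any new or ongoing AEs since the previous visit". Visits are every two weeks during the Treatment Period, and missing data are queried before database lock. This also stands, and it limits the size of the point.

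**First-dose imputation is otherwise a usual conservative choice.** Agreed. The fault is confined to events with a known stop before the first dose.

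**Conclusion.** Both rules are wrong as written. The causality trigger names a dose that does not exist. The start-date rule gives an impossible interval for any event it sends to the first-dose date when the known stop is earlier. The false TEAE follows only if the flag uses the imputed date, and the loss of related events follows only if the trigger is taken literally. The impact is confined to safety tables and is probably small. The number of events affected cannot be computed, because the documents give no rate of partial dates or missing causality.

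A reader might infer more, but the documents do not support it:

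- *An event with unknown month first reported at Week 24 is misclassified when moved to Day 1.* It is post-dose either way and stays a TEAE. SAP 8.8.1 plans incidence tables and listings, not time to onset of adverse events.
- *Such an event becomes an infusion-associated reaction.* The Appendix window runs to four hours after the infusion and needs a clock time; SAP 7.2 imputes only a date. These reactions are also typed by clinical manifestations and reported in listings.
- *Every event with unknown month is affected in an infant born and dosed in the same year.* The rule turns on the first-dose year. Events in other years go to January, and treatment can run to 240 weeks.
- *Each misfiled event moves an incidence by 6.7 points (1/15), or by 20 points among five infants with hydrops (1/5).* An event changes nothing if the child already counts in that row, and no table by hydrops status is planned; SAP 8.1 splits only by emergency-IND treatment.

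**What to change.** Make two changes in SAP 7.2, together:

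1. In the missing-causality rule, replace the reference to double-blind product with *UX003 in this study*, matching the start-date rule and the TEAE definition.
2. Under Missing Start Dates, add: *An imputed start date may not be later than the known stop date. If the stop date precedes the first dose of UX003 in this study, use the earliest date consistent with the known parts (not before birth), and the event is not a TEAE.*

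The cost is a few words, one short clause and minor programming. No data collection changes. Events without a contradicting stop date keep the dates they would get now, as the unchanged rows of the table show.

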### 7.3 Visit Time Windows

Table 7.3–1 presents the visit window assigned for scheduled efficacy and safety assessments scheduled for every 12 weeks and the corresponding range of treatment days (window) during which an actual visit may occur.

**Table 7.3–1. Visit Time Windows**

Period	Visit	Scheduled Visit Day	Window
48-Week Treatment Period	Baseline	Day 1	Days $\leq 1$
	Week 12	Day 85	Days [2, 127]
	Week 24	Day 169	Days [128, 211]
	Week 36	Day 253	Days [212, 295]
	Week 48	Day 337	For subjects entered into continuation period Days [296, start of continuation period-1] For subjects did not enter into continuation period Days $\geq 296$
Continuation Period Weeks 50-240	Week 60	Day 421	Days [start of continuation period, 463]
	Every 12 Weeks	Day $84x^a+421$	[380+84x, 463+84x]
	Week 240	Day 1681	Days $\geq 1640$

a x=1,2...14

End of Treatment visit for subjects who didn't complete either the 48-week treatment period or the continuation period, and unscheduled visits will be mapped to the closest post baseline scheduled visits if the scheduled visits are missing. If there are more than one unscheduled/end of study visits mapped to the same window, the one closer to the target day will be used. If more than one visits have the equal distance to the target day then the later one will be used, if more than one visits on the same day, use the time or the sequence number to select the later record. For listings and shift tables, all data points will be included.

### 7.4 Software

SAS® software version 9.4 or higher will be used to perform most or all statistical analyses.

## 8 STATISTICAL METHODS OF ANALYSIS

### 8.1 General Principles

Due to the small sample size, all raw data obtained from the Case Report Forms (CRFs) as well as any derived data will be included in data listings or graphs. Descriptive statistics will be used to summarize the data. For continuous variables, means, standard deviations, medians, minimums, and maximums will be provided. For categorical variables, the counts and percentages of subjects in corresponding categories will be provided. All analysis will be based on full analysis set. Statistical tests will be 2-sided at the alpha =0.05 significance level. All p-values will be presented as nominal p-values. Summary statistics will be provided separately for subjects treated with UX003 under an emergency IND or not. Combined summaries will only be provided for uGAG and safety analyses, as prior data to initial treatment will be available for uGAG.

### 8.2 Subject Disposition

The subjects in the full analysis set will be listed. Date of informed consent, the reason for treatment discontinuation and study discontinuation will be displayed.

### 8.3 Demographics and Other Baseline Characteristics

Demographic parameters (e.g., age, sex, race and ethnicity) and other baseline characteristics (i.e., initial diagnosis, height and weight) assessed at baseline will be summarized and listed.

### 8.4 Medical History

Medical history and MPS treatment history will be summarized.

### 8.5 Prior and Concomitant Medications

The World Health Organization Drug (WHODRUG) dictionary will be used to classify prior and concomitant medications. Prior medication is defined as any medication taken prior to the first dose of the investigational product in this study. Concomitant medication is defined as any medication taken during the study between the day of the first dose of the investigational product and the day of the last dose of the investigational product in this study. Any medications started after the date of the last dose of the investigational products will not be considered concomitant medications. The number and proportion of subjects receiving each reported concomitant medication will be summarized by Anatomical Therapeutic Chemical (ATC) code and preferred term. Multiple drug usage by a subject in the same category will be counted only once in the summary tables.

### 8.6 Dosing Summary

The number of infusions and cumulative dose per subject administered and duration of exposure to UX003 on this study will be summarized. Treatment compliance calculated as received dose divided by expected dose over specified period will also be displayed.

## 8.7 Efficacy Analyses

### 8.7.1 Primary Efficacy Endpoint

The primary efficacy analysis will evaluate the mean percent change in uGAG excretion from baseline at week 48 using the generalized estimating equation (GEE) analysis method. The model will include baseline and visit (up to week 48) as a categorical variable. The covariance structure within subjects will be assumed to be exchangeable. For subject(s) previously treated with UX003 under an emergency IND, percent change from initial baseline will be calculated.

In addition, the change and percentage change from baseline, fold increase in uGAG excretion and number of uGAG responders (defined as  $\geq 50\%$  decrease in uGAG excretion from baseline) will be presented by visit.

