## **7.6 Statistical Methods and Determination of Sample Size**

The completeness of the data affects the integrity and accuracy of the final study analysis. Therefore, every effort will be made to ensure complete, accurate and timely data collection, and to avoid missing data. Detailed procedures for handling missing, unused, or spurious data, along with the detailed method for analyses will be presented in the Statistical Analysis Plan (SAP); the information below is intended as a guide to planned analyses.

The statistical analyses will be reported using summary tables, figures, and data listings. All raw data obtained from the CRFs as well as any derived data will be included in data listings. All analyses and tabulations will be performed using SAS®. Descriptive statistics will be used to summarize the data. For continuous variables, the mean, standard error, median, minimum, and maximum will be provided. For categorical variables, the frequency and percent distributions will be provided. Statistical tests will be two-sided at the alpha =0.05 significance level. Two-sided 95% confidence intervals will also be presented when appropriate. The statistical method employed for the analysis of each assessment will be defined in more detail in the SAP.

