### **7.6.4 Primary Efficacy Endpoint**

The study is a small open label study to obtain some clinical efficacy data from a small cohort of these ultra-rare patients. A complete hypothesis testing statistical approach is not plausible in this setting, but a reasonable approach to assessing for the biologic efficacy of UX003 will be made.

The primary efficacy analysis will evaluate the mean percent change in uGAG excretion from Week 0 (Baseline) to Week 48 using the generalized estimating equation (GEE) analysis method. For subject(s) previously treated with UX003 under an emergency IND, percent change from initial baseline (prior to first dose of UX003) will be used, if the initial baseline data are available. The null hypothesis of no change in mean uGAG excretion will be tested. An additional analysis will also be performed on the Week 24 time point.

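### The primary Week 48 uGAG GEE on about 15 children names no standard error, small-sample correction or reference distribution; with an uncorrected sandwich error and a normal reference its 95% interval is about 12-16% too narrow

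*SAP*

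**What the plan says.** SAP 8.7.1 will evaluate the "mean percent change in uGAG excretion from baseline at week 48 using the generalized estimating equation (GEE) analysis method". The mean model has baseline and categorical visit, and "The covariance structure within subjects will be assumed to be exchangeable".

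Protocol 7.6.4 adds: "The null hypothesis of no change in mean uGAG excretion will be tested", and "An additional analysis will also be performed on the Week 24 time point". Protocol 7.6 sets the general rules: "Statistical tests will be two-sided at the alpha =0.05 significance level"; "Two-sided 95% confidence intervals will also be presented when appropriate". It passes the detail on: "The statistical method employed for the analysis of each assessment will be defined in more detail in the SAP".

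SAP 8.1 repeats the two-sided 0.05 level and labels all p-values nominal. Its list of summary statistics has no confidence interval. SAP 7.4 names SAS 9.4 or higher but no procedure or option. SAP 3.2 plans about 15 children, about 5 of them with hydrops fetalis, a number set by feasibility. SAP 7.1 generally leaves missing data missing.

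Neither document names a standard-error estimator, a small-sample correction, degrees of freedom, or a normal or t reference for the GEE.

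**The concern.** In this GEE the children are the independent units, and there are about 15. The sandwich standard error is justified for a large number of units. With few, fitted residuals are smaller than the true errors, so it tends to be too small. A normal critical value also ignores the uncertainty in the standard error itself. Both faults narrow the interval.

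Model-based errors behave differently. They apply one pooled variance to all visits, so their accuracy at Week 48 depends on that visit being as variable as the others. Stating that the covariance is exchangeable fixes the working correlation; it does not choose between the two estimators.

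At stake is the interval and nominal test for the primary efficacy endpoint. SAP 3.3 also allows analyses at any time in this open-label study, so an unstated choice could be made after results have been seen.

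**Working it through.** **Stated figure.** The documents give no power, effect size or SD. The only error rate to check is the nominal two-sided 0.05 (critical value 1.960).

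**Inputs from the documents.** About 15 children (SAP 3.2); baseline plus categorical visit, exchangeable (SAP 8.7.1); post-baseline uGAG at Weeks 4, 8, 12, 18, 24, 30, 36, 42 and 48 (Protocol Table 2.1), or only the four 12-weekly windows of SAP 7.3.

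**Assumptions.** Normal data, within-child correlation 0.3-0.8, equal variances, complete data and no baseline effect, unless stated. SDs of 20 and 40 points are illustrative.

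**Closed form, n=15.** Let k be 1 (mean only) or 2 (mean and baseline).
- Sandwich with normal reference: P(|t(n-k)| > 1.960 × √((n-k)/n)). k=1: P(|t14| > 1.893) = 7.9%. k=2: P(|t13| > 1.825) = 9.1%.
- The same formula gives 8.7-10.4% at n=12 and 9.6-11.8% at n=10.
- Model-based with normal reference: P(|t14| > 1.960) = 7.0%.
- Width ratio, sandwich-normal to t interval: 1.893/2.145 = 0.883 (k=1); 1.825/2.160 = 0.845 (k=2). The interval is therefore 12-16% too narrow.

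**Simulation.** The true mean was tested at the sample mean baseline. Main cells have 40,000 runs (Monte Carlo error about 0.15 points); the unequal-variance and baseline-effect cells have fewer (about 5,000-8,000). The corrected columns use t on children with data at that visit minus 2, except where marked *, which used t(14).

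| Scenario | Sandwich, normal | Model-based, normal | Mancl-DeRouen, t | Kauermann-Carroll, t |
|---|---|---|---|---|
| n=15, Week 48 | 8.3-8.8% | 5.7-6.6% | 3.9-4.1% | 4.9-5.1% |
| n=15, Week 24 | 8.6% | 6.3% | 3.9% | 5.0% |
| n=12 | 9.5% | 6.5% | 3.5% | 4.7% |
| n=10 | 10.9% | 7.2% | 3.4% | 4.8% |
| 5 of 15 without Week 48, at random | 9.0-9.9% | 5.7-8.2% | 2.9-3.4% | 3.9-4.5% |
| Week 48 SD 1.5 times other visits | 8-9% | 14-18% | 4.1-4.2%* | 4.7-4.9% |
| Week 48 SD 0.7 times other visits | 8-9% | 1-2% | 3.2-3.9%* | 4.7-4.9% |
| Lognormal ratio, skewness 1.3-1.75 | 10.2-11.0% | 7.2% | 5.3-6.0% | 6.4-7.4% |
| Lognormal ratio, skewness 2.9 | 13.0% | 8.2% | 8.0% | 9.4% |
| Baseline slope 0.3-0.5 residual SD per baseline SD | 9.8-12.6% | 7.4-9.7% | 4.5-6.4%* | 5.5-7.7% |

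A second, smaller set of runs at n=15 with normal data gave 8.3-9.2% (sandwich) and 5.6-6.9% (model-based). An uncorrected sandwich with t(13) still rejects 5.9-6.3%, so a t reference alone does not repair it.

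**Half-widths at n=15.** The t interval is t(0.975, 15-k) × SD/√15; the sandwich-normal interval is that times the ratio above.
- SD 20: t gives 2.145 × 5.164 = 11.1 or 2.160 × 5.164 = 11.2 points; sandwich-normal gives 9.8 or 9.4. Gap 1.3-1.7 points.
- SD 40: t gives 22.2 or 22.3; sandwich-normal gives 19.6 or 18.8. Gap 2.6-3.5 points.

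**Effect on the test against zero.** The two intervals disagree about zero only for an observed mean reduction of 9.4-11.2 points (SD 20) or 18.8-22.3 points (SD 40). A reduction of 50 points is well outside both ranges.

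**The case against.** The strongest reply is that little depends on this test. SAP 8.1 calls p-values nominal, and Protocol 7.6.4 says "A complete hypothesis testing statistical approach is not plausible in this setting". Protocol 7.5.2.1 and the responder definition in SAP 8.7.1 look to reductions around 50%, and neither document compares the interval with that threshold. This stands, and it limits the severity.

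Second, silence does not commit the sponsor to a poor method; a corrected error with a t reference may be intended. That also stands, so every rate above is conditional on a choice the documents leave open.

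Third, the protocol already plans intervals. This stands only in part: it plans them when appropriate and leaves the method to the SAP, which does not mention them.

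A reader might infer that the test exceeds 5% by a modest, known amount whichever standard error is used. The documents do not support that. They specify no normal reference, and the model-based rate can fall to 1-2% or rise to 14-18% depending on the Week 48 variance. A reader might also infer that a finding of uGAG reduction would be unreliable. At reductions near 50%, and at the SDs assumed here, it would not be.

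**Conclusion.** The omission is real and concerns the primary efficacy analysis, but its severity is minor to moderate. The sandwich-normal result is the firmer one: about 8-9% at n=15 with normal data, largely insensitive to correlation and unequal variances, and higher with fewer children, right skew or a baseline effect. The model-based figure of about 6-7% holds only with equal variances across visits. The SDs, correlations, skewness and baseline slopes are assumptions; the documents give none of them. What is gained is a primary-endpoint interval closer to its stated coverage and a method fixed in advance. The conclusion about a large uGAG reduction would not change.

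**What to change.** Keep the endpoint, mean model and exchangeable working covariance in SAP 8.7.1, and add wording such as:

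> The mean percent change at Week 48, evaluated at the mean baseline of all children in the model, will be reported with a two-sided 95% confidence interval and test. Standard errors will be bias-corrected empirical (Mancl-DeRouen). The reference will be a t distribution with degrees of freedom equal to the number of children with uGAG data at Week 48 minus 2. The same rule applies at Week 24, using the number of children with data at that visit.

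Mancl-DeRouen is preferred because it holds the level better under right skew and a baseline effect. Kauermann-Carroll is a less conservative alternative.

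The change needs only SAP text and programming. Relative to sandwich-normal at n=15, the interval widens by about 21-24% (Mancl-DeRouen) or 16-17% (Kauermann-Carroll). With 5 of 15 children missing at Week 48, the widening is about 34% or 25-26%.

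The correction has limits. It brings the level to about 4-5% with normal data and no baseline effect. Under right skew or a baseline-dependent response it lowers the inflation relative to sandwich-normal without reliably removing it. Under strong skew it is not consistently better than model-based-normal: at skewness 2.9, Mancl-DeRouen gives 8.0% and Kauermann-Carroll 9.4%, against 8.2%. It does not address uGAG values that are missing because a child has died.

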### **7.4.5 Method of Assigning Subjects to Treatment Groups**

Eligible subjects will be enrolled in the study and sequentially assigned an identification number. All subjects will receive active treatment (UX003); there is only one treatment group in the study.

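### SAP 8.7.1 adjusts a single arm for baseline uGAG without defining the Week 48 estimate; read at the average baseline, its standard error omits the sampling variation of that average

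*SAP*

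**What the plan says.** Protocol 7.4.5 confirms that "there is only one treatment group in the study". Protocol 7.6.4 sets the target: "The null hypothesis of no change in mean uGAG excretion will be tested". Its sentence on the GEE names no covariate, and Protocol 7.6 leaves the detail to the SAP.

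SAP 8.7.1 supplies that detail. The endpoint is given as "The primary efficacy analysis will evaluate the mean percent change in uGAG excretion from baseline at week 48". On the model it says "The model will include baseline and visit (up to week 48) as a categorical variable", and on the working correlation "The covariance structure within subjects will be assumed to be exchangeable". I read baseline as a covariate and visit as the categorical term, since percent change at baseline is zero by definition.

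SAP 8.1 adds "Statistical tests will be 2-sided at the alpha =0.05 significance level" and "All p-values will be presented as nominal p-values". Protocol 7.6 plans two-sided 95% intervals where appropriate.

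Neither document states how baseline is centred, at what baseline value the Week 48 mean is evaluated, whether the standard error is robust or model-based, or whether a small-sample correction or t reference applies. Neither gives an SD for percent change or its correlation with baseline.

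**The concern.** In a randomised trial, adjusting for baseline sharpens a contrast between arms. Here there is no contrast: the quantity of interest is one mean. When the adjusted mean is read at the sample-average baseline, the usual software default, the fitted model answers a question about children with exactly the baselines that happened to be sampled. The protocol asks about the population of children under 5 with MPS 7. The difference is a variance component, slope² × Var(baseline)/n, that the model's standard error leaves out.

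Some dependence of percent change on baseline is built in, because baseline is the denominator. The population is also heterogeneous and may include about five infants with hydrops fetalis, so stronger dependence cannot be ruled out. At stake is the error bar on the study's primary efficacy estimate. A small-sample correction does not restore the missing component, because it rescales only the residual variance.

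**Working it through.** The documents contain no power calculation, SD or interval to reproduce; the sample size rests on feasibility. The only benchmark is the nominal two-sided 0.05.

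**Inputs.** n=15 (Protocol 7.6.1, approximate). One arm. Nine post-baseline uGAG visits, which I read from Protocol Table 2.1 as Weeks 4, 8, 12, 18, 24, 30, 36, 42 and 48. R2 is not given, so I use a range of 0 to 0.5.

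**Step 1: standard error.** Let σ² be the variance of Week 48 percent change.
- With complete data and centred baseline, the adjusted Week 48 mean at the average baseline equals the raw mean. Its true variance is σ²/n.
- The model uses residual scatter only: σ²(1−R2)/n.
- The ratio of reported to true standard error is sqrt(1−R2).

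**Step 2: a pooled slope.** The model has no baseline-by-visit term, so one slope serves all visits. If dependence on baseline grows in proportion to time, the pooled slope is (222/9)/48 = 24.67/48 = 0.514 of the Week 48 slope. The residual share becomes 1 − R2[1 − (1−0.514)²] = 1 − 0.764·R2. The ratio is then sqrt(0.771) = 0.878 at R2=0.3 and sqrt(0.618) = 0.786 at R2=0.5. The shortfall is 12% and 21%, instead of 16% and 29%.

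**Step 3: size of the test.** For a single visit with normal data and a t reference on 13 df, the size is exactly P(|t13| > 2.160·sqrt(1−R2)). The simulated columns use 20,000 trials, nine visits, complete data, an exchangeable GEE with residual within-child correlation 0.5, and a sandwich variance. Corrected means scaled by n/(n−2) with t on 13 df.

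| R2 | sqrt(1−R2) | Exact, one visit | Corrected, equal slope at all visits | Corrected, slope growing with time | Uncorrected sandwich, normal reference, equal slope |
|---|---|---|---|---|---|
| 0 | 1.000 | 5.0% | 4.8% | 4.3% | 8.9% |
| 0.04 | 0.980 | 5.4% | 5.1% | 5.0% | 9.2% |
| 0.1 | 0.949 | 6.1% | 5.6% | 5.2% | 10.1% |
| 0.3 | 0.837 | 9.4% | 8.4% | 7.3% | 14.1% |
| 0.5 | 0.707 | 15.1% | 14.2% | 10.4% | 21.1% |

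A second run of the corrected test gave 8.8% and 14.8% (equal slope) and 7.4% and 10.2% (growing slope) at R2=0.3 and 0.5. Without baseline, the t-test on the same data rejected 4.7–5.2% throughout, and the uncorrected sandwich rejected about 8% at every R2.

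**Step 4: separating the two sources.** The uncorrected sandwich is already at about 8–9% when R2=0. That part comes from having few clusters. The baseline part is separate and does not fade with sample size: at n=200, simulated size was 9.6% at |correlation| 0.5 (R2=0.25) and 16.8% at 0.7 (R2=0.49), against about 5.5% without baseline.

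**Step 5: plausible R2.** With lognormal uGAG, a three-sample baseline and assumed log SDs, denominator coupling alone gave R2 of 0.00–0.04 in one set of settings. In another, correlations of −0.11 to −0.24 correspond to R2 of 0.01–0.06. Adding assumed drift in true levels over 48 weeks gave correlations of −0.28 to −0.42 (R2 0.08–0.18). An assumed 50% convergence on the log scale gave R2 of 0.19–0.39. Neither document gives evidence for either drift scenario.

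**Step 6: effect on the interval.** Assume SD 20 points, n=15 and an observed mean reduction of 60%.
- The unconditional standard error is 20/√15 = 5.16. The interval is 60 ± 2.145 × 5.16 = 48.9% to 71.1%.
- Conditioned on baseline at R2=0.3, the standard error is 5.16 × 0.837 = 4.32. The interval is 60 ± 2.160 × 4.32 = 50.7% to 69.3%.
- With the growing slope, 5.16 × 0.878 = 4.53 gives 50.2% to 69.8%.

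The narrower intervals exclude 50%, the cut-off for a responder in SAP 8.7.1, only because a variance component was left out.

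**The case against.** The strongest reply is that the defect is conditional. It needs the Week 48 mean to be read at the average baseline, which the SAP does not say, and an R2 well above zero, which the documents do not supply. The one mechanism they establish, baseline as denominator, gives an R2 at which the effect is negligible. That stands. A reader might infer that the primary test over-rejects as written, or that it reaches twice the nominal level. The documents do not support either: the contrast, the standard error and R2 are all unstated, and most of the inflation of an uncorrected sandwich at low R2 is the few-cluster problem.

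A second reply is that little turns on the p-value. The protocol concedes that "A complete hypothesis testing statistical approach is not plausible in this setting", and p-values are nominal. If the reduction is near the 50% benchmark that Protocol 7.5.2.1 takes from other enzyme replacement programmes, then with an assumed SD of 20 points the statistic against zero is 50/5.16 = 9.7 before any understatement. This also stands, and it moves the weight to the interval.

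Third, SAP 8.7.1 already presents percent change by visit, and SAP 8.1 adds means and standard deviations. An unconditional standard error could be worked out from those tables. That softens the point, but the primary analysis would still carry the narrower error bar.

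Reading the visit coefficient at an uncentred baseline is no escape. It would describe a child with zero uGAG.

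**Conclusion.** The point holds as a gap in specification with a known direction of error. If the Week 48 mean is read at the sample-average baseline, the covariate gains no precision for the stated target with complete data and can only understate the error bar. The understatement is at most the factor sqrt(1−R2): 5% at R2=0.1, 16% at 0.3, 29% at 0.5, and less where dependence builds up over time. With a small-sample-corrected test at n=15, size is about 5.5% (up to 6.1% in the one-visit formula), 7–9% and 10–15% at those values, and about 5% at R2 up to 0.04. These figures rest on an assumed R2, an assumed contrast and approximately normal data. The practical consequence is a Week 48 interval that is too narrow; a changed conclusion against zero is unlikely. This is a low-cost improvement, not a flaw that invalidates the analysis.

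**What to change.** In SAP 8.7.1, define the primary estimate as the marginal mean percent change at Week 48 in the population, and name one of these in advance:

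- **Drop baseline from the primary model**, with a small-sample-corrected standard error and t reference, and keep the baseline-adjusted model as a sensitivity analysis. In simulation at n=15, the corrected test without baseline had size 4.5–5.0% across correlations of 0 to 0.7.
- **Keep baseline** and take the standard error from a leave-one-child-out jackknife that recomputes the average baseline in each replicate, with t on n−1 df. With 20% early dropout, simulated size was 4.5–5.9% for R2 from 0 to 0.5.

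The two agree with complete data but not necessarily when visits are missing, which SAP 7.1 leaves as missing. That is why the choice must be made beforehand. Dropping baseline without the small-sample correction would leave size at about 8%.

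The cost is one or two sentences in the SAP, a few lines of code and no new data. The interval becomes wider, by 1/sqrt(1−R2) at most: about 5% at R2=0.1, 20% at 0.3 and 41% at 0.5. If baseline is dropped, the model also loses baseline information for children without a Week 48 value. This matters in a study that expects high mortality among infants with hydrops.
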